5.4.1 Acceptable Concomitant Medications

All treatments that the investigator considers necessary for a subject's welfare may be administered at the discretion of the investigator in keeping with the community standards of medical care. All concomitant medication will be recorded on the case report form (CRF) including all prescription, over-the-counter (OTC), herbal supplements, and IV medications and fluids. If changes occur during the trial period, documentation of drug dosage, frequency, route, and date may also be included on the CRF.

Intrathecal methotrexate or cytarabine may be administered for central nervous system prophylaxis at the clinician's discretion.

All concomitant medications received within 28 days before the first dose of trial treatment and 30 days after the last dose of trial treatment should be recorded. Concomitant medications administered are to be recorded after 30 days after the last dose of trial treatment should be recorded for SAEs and ECIs as defined in Section 7.2.

5.4.2 **Prohibited Concomitant Medications**

Subjects are prohibited from receiving the following therapies during the Screening and Induction Phase of this trial:

- Chemotherapy not specified in this protocol
- Investigational agents other than mosunetuzumab, polatuzumab vedotin, and obinutuzumab
- Radiation therapy (may be administered more than 30 days after last dose of study therapy if planned for consolidation)
- Live vaccines within 30 days prior to the first dose of trial treatment and while participating in the trial. Examples of live vaccines include, but are not limited to, the following: measles, mumps, rubella, chicken pox, yellow fever, rabies, BCG, and typhoid (oral) vaccine. Seasonal influenza vaccines for injection are generally killed virus vaccines and are allowed; however intranasal influenza vaccines (e.g. Flu-Mist®) are live attenuated vaccines, and are not allowed.
- SARS-CoV-2 vaccines (mRNA, inactivated virus, and replication deficient viral vector vaccines) Concomitant administration of an approved non-live SARS-CoV-2 vaccine is permitted. Examples of permitted vaccines include mRNA, inactivated virus, and replication-deficient viral vector vaccines. The decision whether and when to administer a SARS-CoV-2 vaccine should be individualized by the investigator in consultation with the patient. Factors to consider when making the individualized decision for patients receiving mosunetuzumab include the following:
 - Risk of SARS-CoV-2 infection and potential benefit from the vaccine
 - General condition of the patient and potential complications associated with SARS-CoV-2 infection
 - Severity and seriousness of the underlying disease
 - Epidemiology of COVID-19 in the patient's location

Prior to starting study treatment, SARS-CoV-2 vaccines and other permitted vaccines should ideally be administered to patients before the start of immunosuppressive therapy, with the aim to complete the vaccination course at least one week prior to starting study treatment, unless a delay is clinically unacceptable.

If a SARS-CoV-2 vaccine is administered while the patient is already receiving study treatment, administration of the vaccine should be timed

to take place after completion of mosunetuzumab step-up dosing and at least one week after administration of the target dose.

The SARS-CoV-2 vaccine should be administered in the middle of a treatment cycle, for example one week before or after a dose of mosunetuzumab. Cytokine-release syndrome (CRS) is a risk for mosunetuzumab that occurs most commonly during step-up dosing. Many SARS-CoV-2 vaccines are highly immunogenic, and their risk of potentiating CRS is unknown.

In vitro data suggest that unconjugated MMAE is mainly metabolized by CYP3A4 and, to a lesser extent, by CYP2D6. Based on a validated physiological-based PK model simulation, strong CYP3A4 inhibitors may increase the exposure (e.g., area under the concentration–time curve) of unconjugated MMAE by ~50% while acMMAE PK is not affected.

If a patient is taking any of the medications in the categories of strong CYP3A4 inhibitors and inducers, the investigator will assess and document the use of these medications known or suspected to fall in those categories. A sample list of cautionary medications that fall into the categories within this section can be found in Appendix Section 14.4. The lists of medications are not necessarily comprehensive. The investigator should consult the prescribing information when determining whether a concomitant medication can be safely administered with study treatment. Patients are prohibited from using strong CYP3A4 inhibitors in part B of the study, and as discussed in the inclusion/exclusion criteria, patients may need to wash out these medications before proceeding with part B of the study. In addition, the investigator should contact Subjects who, in the assessment by the investigator, require the use of any of the aforementioned treatments for clinical management should be removed from the trial. Subjects may receive other medications that the investigator deems to be medically necessary. The Exclusion Criteria describes other medications which are prohibited in this trial.

Mosunetuzumab: Given the expected pharmacology of mosunetuzumab, the transient release of cytokines (most resolved within the first 24 hours of the C1D1 dose) may suppress CYP450 enzymes and cause drug-drug interactions. Preliminary clinical data indicate that mosunetuzumab induced a transient elevation in plasma IL-6, with peak levels occurring in the majority of patients within 4-6 hours of the C1D1 dose, and returning to baseline by 24 hours. Patients may be of highest risk of a drug-drug interaction are those receiving concomitant medications that are CYP450 substrates and have a narrow therapeutic index (Appendix 14.4). Such concomitant medications should be monitored for

toxicity, and dose adjusted accordingly.

A sample list of cautionary medications that fall into the categories within this section can be found in Appendix Section 14.4. The lists of medications are not necessarily comprehensive. The investigator should consult the prescribing information when determining whether a concomitant medication can be safely administered with study treatment. In addition, the investigator should contact the principal investigator if questions arise regarding medications not listed above.

MMAE is a P-glycoprotein (P-gp) substrate but not a P-gp inhibitor. Concomitant medications that are P-gp inhibitors (Appendix Section 14.4) should be considered cautionary as they may potentially lead to adverse reactions, which require close monitoring. If a patient is taking any of the medications in the categories of P-gp inhibitors, the investigator will assess and document the use of these medications known or suspected to fall in those categories. A sample list of cautionary medications that fall into the categories within this section can be found in Appendix Section 14.4. The list of medications is not necessarily comprehensive.

5.5 Supportive Care

Subjects should receive appropriate supportive care measures as deemed necessary by the treating investigator. For each disorder, attempts should be made to rule out other causes such as metastatic disease or bacterial or viral infection, which might require additional supportive care.

It may be necessary to perform conditional procedures such as bronchoscopy, endoscopy, or skin photography as part of evaluation of the event.

5.5.1 Additional Events of Clinical Interest

An overdose of Sponsor's product, as defined in Section 7.2.1 - Definition of an Overdose for This Protocol and Reporting of Overdose to the Sponsor, that is not associated with clinical symptoms or abnormal laboratory results.

5.6 Diet/Activity/Other Considerations

5.6.1 Diet

Subjects should maintain a normal diet unless modifications are required to manage an AE such as diarrhea, nausea or vomiting.

5.6.2 Contraception

The study agents may have adverse effects on a fetus in utero. Furthermore, it is not known if the study agents have transient adverse effects on the composition of sperm.

Women of childbearing potential must agree to remain abstinent (refrain from heterosexual intercourse) or use contraceptive methods that result in a failure rate of < 1% per year during the treatment period and for at least 12 months after the last dose of study treatment. Women must refrain from donating eggs during this same period. A woman is considered to be of childbearing potential if she is post-menarcheal, has not reached a postmenopausal state (≥ 12 continuous months of amenorrhea with no identified cause other than menopause), and has not undergone surgical sterilization (removal of ovaries and/or uterus). The definition of childbearing potential may be adapted for alignment with local guidelines or requirements. Examples of contraceptive methods with a failure rate of < 1% per year include bilateral tubal ligation, male sterilization, hormonal contraceptives that inhibit ovulation, hormone-releasing intrauterine devices, and copper intrauterine devices.

The reliability of sexual abstinence should be evaluated in relation to the duration of the clinical trial and the preferred and usual lifestyle of the patient. Periodic abstinence (e.g., calendar, ovulation, symptothermal, or post-ovulation methods) and withdrawal are not acceptable methods of contraception.

Men must agree to remain abstinent (refrain from heterosexual intercourse) or use a condom, and agree to refrain from donating sperm, as defined below: With female partners of childbearing potential or pregnant female partners, men must remain abstinent or use a condom during the treatment period and for at least 5 months after the last dose of polatuzumab vedotin. Men must refrain from donating sperm during this same period.

The reliability of sexual abstinence should be evaluated in relation to the duration of the clinical trial and the preferred and usual lifestyle of the patient. Periodic abstinence (e.g., calendar, ovulation, symptothermal, or postovulation methods) and withdrawal are not acceptable methods of preventing drug exposure. Male patients considering preservation of fertility should bank sperm before study treatment.

Subjects should be informed that taking the study medication may involve unknown risks to the fetus (unborn baby) if pregnancy were to occur during the study. In order to participate in the study they must adhere to the contraception requirement (described above) for the duration of the study and during the follow-up period defined in section 7.2.2-Reporting of Pregnancy and Lactation to Genentech. If there is any question that a subject will not reliably comply with the requirements for contraception, that subject should not be entered into the study.

5.6.3 Use in Pregnancy

If a subject inadvertently becomes pregnant while on study treatment, the subject will immediately be removed from the study. The outcome of the pregnancy will be reported to Genentech without delay and within 2 business days of investigator knowledge if the outcome is a serious adverse experience (e.g., death, abortion, congenital anomaly, or other disabling or life-threatening complication to the mother or newborn). The study investigator will make every effort to obtain permission to follow the outcome of the pregnancy and report the condition of the fetus or newborn to Genentech. If a male subject impregnates his female partner the study personnel at the site must be informed immediately and the pregnancy reported to Genentech and followed as described above and in Section 7.2.2.

5.6.4 Use in Nursing Women

It is unknown whether polatuzumab vedotin is excreted in human milk. Since many drugs are excreted in human milk, and because of the potential for serious adverse reactions in the nursing infant, subjects who are breast-feeding are not eligible for enrollment.

5.7 Subject Withdrawal/Discontinuation Criteria

Subjects may withdraw consent at any time for any reason or be discontinued from the trial at the discretion of the investigator. In addition, a subject may be withdrawn by the investigator if enrollment into the trial is inappropriate, the trial plan is violated, or for administrative and/or other safety reasons. Subjects who require cessation of study therapy but do not withdraw consent may remain in standard follow-up for up to 5 years.

A subject must be discontinued from study therapy for any of the following reasons:

- The subject or legal representative (such as a parent or legal guardian) withdraws consent.
- Confirmed disease progression except as outlined in section 5.2
Note: A subject may be granted an exception to continue on treatment with radiographic progression if clinically stable or clinically improved, at clinician discretion
- A required dose delay of more than 14 days except with permission of the principal investigator
- Adverse experiences deemed unacceptable by the investigator, including those described in Section 5.2 and Table 5
- Investigator's decision to withdraw the subject
- The subject has a confirmed positive serum pregnancy test

- Noncompliance with trial treatment or procedure requirements
- The subject is lost to follow-up
- Administrative reasons

Subjects who discontinue for reasons other than progressive disease will complete end of treatment visit within 14 days of the decision to remove the subject from the study, but may be waived or performed at a later date at the discretion of the principal investigator. These subjects ideally will undergo end of treatment blood testing and response assessment as outlined in the schedule of events. Subjects should be seen 4-6 weeks after last dose of study medication for off study visit and AE assessment (may be combined with end of treatment visit). These subjects ideally will undergo end of treatment blood testing and response assessment as outlined in the schedule of events. However, all patients may have post-treatment follow-up for disease status up to 5 years at longest.

For those with unacceptable adverse experiences grade 3 or higher related to one of the study agents, follow-up on study until resolution to grade or stabilization of toxicities is required up to a maximum of 1 year from occurrence of the toxicity.

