Subjects who must permanently discontinue mosunetuzumab monotherapy due to toxicity should have a response assessment with positron emission tomography (PET)/CT as soon as is clinically feasible and be evaluated for consideration of treatment in Part B as outlined below. These subjects would then be realigned to cycle 9 day 1 provided at least 21 days \pm 2 days have passed since the last mosunetuzumab injection

Subjects will undergo a computed tomography (CT) between cycle 4 day 1 and cycle 5 day 1. Those with at least stable disease (SD) or better by Lugano²³ criteria will proceed with treatment for cycles 5-8. Subjects with progressive disease (PD) at this timepoint may proceed with cycles 5-8 if the investigator assesses that the subject is deriving clinical benefit from the study medication (e.g. pseudoprogression). If there is no clinical benefit to this medication seen in patients with PD, subjects should receive additional therapy outside of the protocol.

Imaging with a PET/CT will be performed between cycle 8 day 1 and cycle 9 day 1. Subjects in a complete remission (CR) will not receive any further study therapy and will be observed in long term follow up. For this response assessment, a Deauville score will be assigned by the clinical radiology read. If the sub-investigator or principal investigator disagrees with the Deauville score assigned, another nuclear medicine physician will adjudicate the results.

All other subjects who do not achieve a CR may proceed with Part B of study treatment. Those with progressive disease (PD) may proceed with Part B only if they are deriving clinical benefit from the treatment (e.g., pseudoprogression, mixed response overall reduction in tumor) after discussion with the Principal Investigator.

Mosunetuzumab Dose Modifications/Toxicity Management

Administration of mosunetuzumab will be performed in a clinical setting with immediate access to a code team staff who are trained to monitor for and respond to medical emergencies. Additional management may take place after transfer to the University of Washington Medical Center, where there is access to neurology and nephrology consultation services in the event of cytokine release syndrome and tumor lysis syndrome, respectively.

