Dosing delays exceeding 14 days in the initiation of the next planned cycle of treatment will require study treatment discontinuation unless principal investigator approval is obtained to continue on study treatment.

Patients should permanently discontinue polatuzumab vedotin if further dose reduction is indicated beyond 1.4 mg/kg. In this case, subjects may still continue to receive obinutuzumab monotherapy through cycle 14.

If an individual study drug (obinutuzumab or polatuzumab vedotin) is omitted during a cycle for any reason including toxicity while the other drug is administered, the omitted drug will not be made up at a later date.

Patients discontinuing individual agents should remain in the study and continue with all protocol-defined assessments and treatments.

Patients who discontinue all study treatment for adverse events should continue to have disease assessments per institutional standard of care.

GCSF may be administered at the discretion of the investigator for persistent neutropenia resulting in delay of treatment

Tumor Lysis Syndrome

As many patients will have partially treated lymphoma by Cycle 9 day 1, additional tumor lysis syndrome prophylaxis will be at the discretion of the investigator based on most recent imaging and laboratory values.

Table 5: Dose interruptions, reductions, and discontinuations of study agents

Event(s)	Dose delay or modification
Grade 3 or 4 neutropenia on day 1 of cycle 10-14 with or without infection or fever, first delay ^a	
 • Delay all study treatment for a maximum of 14 days. • When ANC recovers to $\geq 1000/\mu\text{L}$, Polatuzumab vedotin dosing should remain t
Recurrent Grade 3 or 4 neutropenia on day 1 of cycle 11-14 with or without infection or fever	
 • Delay all study treatment for a maximum of 14 days. • If ANC recovers to $\geq 1000/\mu\text{L}$ within 7 days of day 1, Resume at same dose. If g required for neutrophil recovery, then next doses of polatuzumab vedotin dosing s GCSF use is at the discretion of the investigator, but recommended for subjects w interruption due to neutropenia.

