4. Screening bone marrow biopsy and aspirate may be completed up to 12 weeks prior to study enrollment, and at time of CR (as close to date of CR as possible). Bone marrow biopsy may be waived at the discretion of the Principal Investigator.
5. See Section 7.1.4. Other procedures during screening are at the discretion of the treating investigator and may include standard-of-care assessments, central venous catheter placement, laboratory studies, or other measures.
6. The presence of archival tissue will be assessed during screening, and unstained slides may be collected. When available this tissue will be provided for central biobanking.
7. Baseline correlative blood draw (eg. For ctDNA measurements) may be done at any time prior to the C1D1 dose. Additional correlative timepoints will be collected at baseline, as well as around the time of any response assessment. Correlative blood draws should also be performed for the end of treatment or off study visit in patients who do not achieve CR at assessment. Additional timepoints may be drawn at the time of other expected blood draws at the discretion of the investigator.
8. See Table 8 for details of these tests.
- 9: End of treatment visit should be scheduled at the time of the expected cycle 9 day 1, or within 14 days of removal from protocol. Subjects who are not in CR and do not proceed with Cycle 9 Day 1 of polatuzumab vedotin and obinutuzumab as outlined in section 5.2 and 6.2.
10. Study-mandated visits are not required, but the study team may query records to assess disease status or vital status for up to 5 years after completion of therapy. Patients on alternative therapy should have AEs recorded for up to 30 days after last dose of study therapy or first administration of alternate therapy, whichever comes first.
11. Monitoring for tumor lysis syndrome should be performed on cycle 1 day 2. Liver function testing is optional. Additional supportive care and monitoring can be provided as determined by baseline testing and risk factors.

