7.1.5 Withdrawal/Discontinuation

When a subject discontinues/withdraws prior to trial completion, all applicable activities scheduled for the final trial visit should be performed at the time of discontinuation. Any adverse events which are present at the time of discontinuation/withdrawal should be followed in accordance with the safety requirements outlined in Section 7.2 - Assessing and Recording Adverse Events.

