7.1.6.3 End of Treatment/Off Study Visit

At the completion of Part A, subjects will undergo a response assessment and clinic visit at the time of a possible cycle 9 day 1. For subjects with a CR, the visit that day will be called an end of treatment visit with labs/assessments outlined in section 6.1. An additional off-study visit 4-6 weeks after last dose of study drug will be required as well.

For subjects who do not achieve a CR in Part A and are eligible to proceed to Part B, Cycle 9 Day 1 will occur instead of an end of treatment visit. An off study visit alone will occur in lieu of an end of treatment visit 4-6 weeks after the last dose of study therapy. This visit will include review of tumor imaging (FDG PET-CT) as well as medical history, physical exam, and laboratory evaluations required for determination of remission status. Patients who come

off study early due to suspected progression or toxicity should have a clinic visit and tumor imaging as soon as it can be safely performed. Subjects who discontinue mosunetuzumab due to toxicity may undergo a response assessment, and if not in a CR, may proceed with part B. Remission status is to be determined according to 2014 Criteria (“The Lugano Classification”)²³ as in Appendix 14.3.

For patients with equivocal post-induction imaging or clinical findings, in whom remission status cannot be clearly ascertained, further workup as per clinical standard of care including tumor biopsy or repeat imaging should be undertaken to confirm remission status (PR or CR) prior to proceeding onto the Follow-Up Period

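### For subjects who stop early without progression, the protocol's rules on response imaging conflict and partly leave it to discretion, and Section 8 drops never-assessed subjects from the CR denominator

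*Combined protocol and SAP*

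**What the plan says.** The rules for a subject who stops early are spread over several sections, and none is given precedence.

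- **5.7** (stopping for reasons other than progression): the end-of-treatment visit is due within 14 days of the decision, "but may be waived or performed at a later date at the discretion of the principal investigator". On the response assessment: "These subjects ideally will undergo end of treatment blood testing and response assessment as outlined in the schedule of events". A separate off-study visit 4 to 6 weeks after the last dose carries no waiver.
- **7.1.5** (any early discontinuation): "all applicable activities scheduled for the final trial visit should be performed at the time of discontinuation".
- **7.1.6.3** (off early for suspected progression or toxicity): these patients "should have a clinic visit and tumor imaging as soon as it can be safely performed". The next sentence reads: "Subjects who discontinue mosunetuzumab due to toxicity may undergo a response assessment".
- **5.3, Part A** (mosunetuzumab permanently stopped for toxicity): these subjects "should have a response assessment with positron emission tomography (PET)/CT as soon as is clinically feasible".
- **6.1, footnote 9**: the end-of-treatment visit falls at the expected start of cycle 9, "or within 14 days of removal from protocol". The Part A chart marks tumor imaging in that visit's column.
- **5.3, Parts A and B**: "Patients who discontinue all study treatment for adverse events should continue to have disease assessments per institutional standard of care".

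Section 8 makes a subject efficacy evaluable after one response assessment. Subjects who leave treatment before any assessment are not evaluable and not replaced. If fewer than 42 are evaluable, the 80% CR goal is re-applied to those who are. The trial is open label (5.3.2) and scans are read locally without central review (7.1.2.5).

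**The concern.** The instructions for the same subject run from imaging at discontinuation, through imaging when feasible, to imaging that is ideal, optional or attached to a visit that can be waived. A site can follow one section and breach another.

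This reaches the primary endpoint through Section 8. The first scheduled on-treatment scan is the CT between day 1 of cycle 4 and day 1 of cycle 5. For a subject who stops before it without progression, the only response assessment may be the one that 5.7 leaves open. If it is not done, the subject leaves the denominator and the number of CRs needed for success falls. The person who can waive the visit knows the subject's course.

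Section 8 also has no scoring rule for a subject who had an earlier scan but no end-of-treatment scan. That matters if the secondary endpoint is end-of-treatment ORR, as in Section 3. Section 8 names best ORR instead.

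**Working it through.** **Inputs.** N = 42; success is an observed CR rate of at least 80%, that is 34 or more of 42; the 80% goal is re-applied if fewer are evaluable (all Section 8). The documents give no rate of never-assessed subjects, so their number k is an assumption, shown from 0 to 5.

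**Step 1: reproduce the plan's table.** P(X ≥ 34) = Σ C(42, x) p^x (1 − p)^(42 − x), summed over x = 34 to 42. For p = .65, .70, .75, .80, .85, .90 this gives .019, .080, .243, .531, .831, .979. Section 8 prints .02, .08, .24, .53, .83, .98, so the table reproduces.

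**Step 2: threshold when k subjects are dropped.** With n = 42 − k, the required number of CRs is the smallest r with r/n ≥ 0.80. For k = 2: 0.80 × 40 = 32, so r = 32. With all 42 in the denominator, 32/42 = 76%, which fails.

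**Step 3: chance of success at a true CR rate of 80%.** Dropped: P(X ≥ r) with X ~ Bin(42 − k, 0.80). Counted as non-CR: P(X ≥ 34) with the same X, because the remaining subjects must supply all 34.

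| k | Needed if dropped | As share of 42 | Chance, dropped | Chance, counted as non-CR |
|---|---|---|---|---|
| 0 | 34/42 | 81% | 0.53 | 0.53 |
| 1 | 33/41 | 79% | 0.56 | 0.41 |
| 2 | 32/40 | 76% | 0.59 | 0.29 |
| 3 | 32/39 | 76% | 0.47 | 0.18 |
| 4 | 31/38 | 74% | 0.50 | 0.10 |
| 5 | 30/37 | 71% | 0.53 | 0.045 |

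The dropped column is not monotone because the threshold is a whole number. Dropping subjects therefore does not always raise the chance above 0.53, but for every k from 1 to 5 it is well above the chance with the same subjects counted as non-CR. If the k subjects were all scanned and had the same 80% chance of CR as the rest, the chance would stay at 0.53, so for k = 2 the scanned case lies between 0.59 and 0.29. At a true CR rate of 75% and k = 2, the chances are 0.30 dropped and 0.10 counted as non-CR.

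**Step 4: subjects with an earlier scan.** They remain evaluable under Section 8, so the denominator does not move. If the earlier scan was not a CR, a missed scan can forfeit a CR, while a late one can show either a CR or progression. The direction is not fixed and no figure is attached to it.

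**The case against.** Much can be said for the plan, and most of it limits the point.

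- **A reader might infer that the principal investigator may waive the response assessment itself, for anyone.** The text does not say so. The waiver attaches to the end-of-treatment visit and covers only stoppers without progression. What stands is that the Part A chart puts the imaging in that visit and that 5.7 separately makes the assessment only ideal.
- **A reader might infer that a Part B stopper's scan can be put off indefinitely.** Section 7.1.6.3 gives Part B subjects an off-study visit 4 to 6 weeks after the last dose that includes review of PET/CT, and nothing waives it.
- **A reader might infer a large swing in ORR.** With 2 to 6 stoppers assumed, scoring an earlier PR as non-response or carrying it forward differs by 2/42 to 6/42, or 4.8 to 14.3 points. Under Section 8's best ORR an earlier PR counts by definition and the swing is zero.
- **A reader might infer that one postponed scan lifts the chance of success from 0.53 to 0.68.** That adds P(X = 33) = 0.145 to 0.531. It is a ceiling in one direction: every trial with 33 CRs would need a stopper who converts only because the scan was late.
- **The rules overlap less than a count suggests.** The standard-of-care sentence in 5.3 reads naturally as follow-up after stopping, and imaging at discontinuation or when safe can fall within 14 days.
- **There are safeguards.** Disagreements over a PET/CT read are adjudicated (5.3, 7.1.2.5). This is a pilot without a hypothesis test, and 80% is a loose benchmark read together with other endpoints and toxicity.

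One further limit: Section 8 can be read as making anyone who leaves treatment before an assessment non-evaluable even if scanned afterwards. On that reading the smaller denominator arises from early stopping itself and not from the choice to scan. Section 8's one-assessment definition points the other way, and the remedy is the same.

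**Conclusion.** The point holds in a limited form. The instructions on response imaging after early stopping without progression conflict, and some make it discretionary. Because Section 8 drops never-assessed subjects and re-applies the 80% goal, that choice can decide whether the benchmark is met. With two such subjects, 32 CRs pass (32/40 = 80%) where 32/42 = 76% would not, and at a true CR rate of 80% the chance of success is 0.59 with them dropped against 0.29 with them counted as non-CR.

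These figures assume the value of k, independent subjects with a common CR rate, and the reading of Section 8 under which a scan after stopping makes a subject evaluable. The documents do not support a claim that CR or ORR will be biased in a known direction, that a subject with an earlier scan is dropped, or that the ORR effect survives if best ORR is the secondary endpoint. The change should be made, but this is not a demonstrated bias.

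**What to change.** **Protocol.** Reconcile 5.7, 7.1.5, 7.1.6.3, 5.3 and the flow-chart footnotes into one rule. Any waiver covers the clinic visit only. The response imaging already scheduled is done within one stated window, which can be aligned with the existing 14-day visit or the 4-to-6-week off-study visit, and before new anti-lymphoma therapy. The rule should keep room for the repeat imaging or biopsy that 7.1.6.3 calls for when findings are equivocal.

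**Section 8.** Put every treated subject in the primary denominator, and score a subject with no qualifying CR documented by the end of that window as non-CR. This matches Section 8's own statement of the success criterion, which refers to patients treated. State whether the secondary endpoint is end-of-treatment ORR (Section 3) or best ORR (Section 8). If end-of-treatment ORR is kept, score a missing end-of-treatment assessment as non-response.

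**Cost.** Wording changes only, with no new type of scan. The reported CR and ORR may be slightly lower.
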